A low pH step and a nanofiltration step were used for virus inactivation and reduction. Viral clearance studies used the model viruses PPV and A-MuLV. Testing for adventitious agents was performed in accordance to FDA Points to Consider in the Manufacture and Testing of Monoclonal Antibody Products for Human Use (1997). The clinical trial product was formulated as a single-use sterile solution intended for parenteral use.

Similarly to 3BNC117, a drug product stability-testing program is established to monitor the quality of 10-1074 over the duration of the clinical dosing period. Stability is evaluated in real time at the recommended storage conditions of $5 \pm 3^{\circ}$ C as well as at accelerated temperature conditions of $25 \pm 2^{\circ}$ C / $60 \pm 5^{\circ}$ RH.

3.4.3 Preclinical Toxicity Studies with 10-1074

3.4.4 Clinical Experience with 10-1074

10-1074 is being evaluated in a phase 1 study in both HIV-uninfected and HIV-infected participants (protocol MCA-885). Study participants are administered one intravenous infusion of 10-1074 at increasing dose levels (3 mg/kg, 10 mg/kg or 30 mg/kg), and are followed for 24 weeks after infusion.

As of 12 January 2016, 23 participants (12 HIV-uninfected, 8 viremic HIV-infected and 3 ART-treated HIV-infected individuals) have enrolled in the study. Eleven participants (6 HIV-uninfected and 5 HIV-infected) were administered one dose of 30 mg/kg. 10-1074 has been generally safe and well tolerated at all doses tested. Most common reported adverse event reported to data was fatigue.

Preliminary pharmacokinetics data show that 10-1074's half-life in HIV-uninfected individuals is approximately 15.5 days. Similarly to 3BNC117, 10-1074 has been generally safe and well-tolerated. When administered at 10 mg/kg, 10-1074 reduced plasma viremia by an average of 1.38 log₁₀ copies/ml (n = 3, range 1 – 1.56 log₁₀ copies/ml). At 30 mg/kg, 10-1074 led to similar decline in plasma HIV-1 RNA in the 4 out of 5 participants enrolled to date (n = 4, average 1.37 log₁₀, range 1 – 1.7 log₁₀ copies/ml). One participant dosed at 30 mg/kg experienced a 0.4 log₁₀ decline in viremia. The baseline sensitivity of this participant's plasma viruses to 10-1074 is not yet known. The study remains open to enrollment, and safety, PK and antiretroviral activity data are being collected.

3.5 Objectives

Primary Objectives:

- To evaluate the safety and tolerability of a single intravenous infusion of the combination of 3BNC117 and 10-1074 at 10mg/kg in HIV-uninfected participants.
- To evaluate the safety and tolerability of three intravenous infusions of the combination of 3BNC117 and 10-1074, administered at 3 mg/kg and 10 mg/kg to HIV-uninfected participants.
- To determine the pharmacokinetic profile of intravenous administration of the combination of 3BNC117 and 10-1074 in HIV-uninfected participants.

Secondary Objective:

- To assess the frequency and magnitude of induced anti-3BNC117 and anti-10-1074 antibodies.

Exploratory Objective:

- To evaluate the serum neutralizing activity of the combination of 3BNC117 and 10-1074.

3.6 Outcomes

Primary Outcomes:

- The rate of signs, symptoms and laboratory abnormalities, in addition to local and systemic reactogenicity adverse events 1 week after the combination of 3BNC117 and 10-1074 infusion in all study groups.
- The pharmacokinetic profile of 3BNC117 and 10-1074: elimination half-life (t_{1/2}), clearance (CL/F), volume of distribution (Vz/F), AUC and decay curve in all study groups.

Secondary Outcomes:

- Frequency and levels of induced anti-3BNC117 and anti-10-1074 antibodies at 8 weeks after each infusion in all study groups.
- The rate of signs, symptoms and laboratory abnormalities that occur during study follow up after 3BNC117 and 10-1074 infusions in all study groups.

Exploratory Outcome:

- Neutralization activity of serum from study participants against a panel of viruses as measured by the TZM.bl neutralization assay.

[figure not shown]
4 Study Design

This is a phase 1 clinical trial to evaluate the safety and pharmacokinetics of the highly neutralizing anti-HIV-1 monoclonal antibodies 3BNC117 and 10-1074, when given in combination, in HIV-uninfected individuals. This study is intended to support the development of the combination of 3BNC117 and 10-1074 mAbs for use as prophylaxis against HIV infection in healthy HIV-uninfected individuals at risk for HIV infection.

The study will be conducted under a placebo-controlled, double blind, randomized allocation of the study products. Study participants in each study group will be randomized to receive intravenous infusions of 3BNC117 and 10-1074 or placebo. 3BNC117 and 10-1074 will be administered at 2 dose levels (3 mg/kg and 10 mg/kg). These doses were selected based on the planned development of subcutaneous formulations for the prophylactic use of these products. The study will consist of 3 groups (Figure 1). Enrollment in Group 1 will begin first and participants will be enrolled at least one day apart. Eight participants will be enrolled in each group; 6 will be randomized receive the study drugs and 2 will be randomized to receive placebo. Participants in Group 1 will receive a single infusion of each antibody at 10mg/kg at Week 0. Enrollment in Group 2 will begin only after Day 28 safety data from all participants in Group 1, including ophthalmologic exams, are available. Enrollment in Group 3 will begin only after the Day 28 safety data from all participants in Group 2 is available. If > 1 grade 3 or higher adverse events deemed probably or definitely related to the study drugs occurs in a single group, the next group will not be enrolled pending SMC review. Participants in Groups 2 and 3 will receive 3 infusions of each antibody at

Weeks 0, 8, and 16, at a dose of either 3mg/kg or 10mg/kg. The antibodies will be administered sequentially via intravenous infusion. Each antibody will be administered over 60 minutes.

Figure 1. Study Design

* Enrollment in subsequent group may begin following review of Day 28 safety data from all subjects in the previous group

Following product infusions, study participants will return for safety assessments at multiple time points. Blood samples will be collected for safety testing at weeks 1, 2, and 4 following each infusion, then at multiple time points until the end of study follow up.

Baseline pharmacokinetic assessments will be performed before the start of the first infusion. Peak PK sampling for 3BNC117 will occur following the completion of the 3BNC117 infusion prior to the start of the 10-1074 infusion. Peak PK sampling for 10-1074 will occur following the completion of the 10-1074 infusion. Additional PK assessments will occur at multiple time points during study follow up, as outlined in **Appendix A**. Study participants will be followed for a total of 24 weeks following the final antibody infusion.

5 Study Population

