3.3.3 Preclinical Toxicity Studies with 3BNC117

3.3.4 Clinical Experience with 3BNC117

3BNC117 was evaluated in a phase 1 study in both HIV-uninfected and HIV-infected participants (protocol MCA-835) and is currently being tested in two ongoing exploratory phase 2a studies in HIV-infected participants (protocols MCA-867 and MCA-866).

In protocol MCA-835, study participants were administered one or two intravenous infusions of 3BNC117 at increasing dose levels (1 mg/kg, 3 mg/kg, 10 mg/kg or 30 mg/kg), and were followed for 24 weeks after last infusion. In total, 55 participants (22 HIV-uninfected, 17 viremic HIV-infected and 16 ART-treated HIV-infected individuals) were enrolled in the study. Five HIV-uninfected individuals received two infusions of 3BNC117 at 30 mg/kg, 12 weeks apart. Twenty-two participants (3 HIV-uninfected and 19 HIV-infected) were administered one dose of 30 mg/kg.

Overall, 3BNC117 was generally safe and well-tolerated, mild transient myalgia, fatigue and headache were the most commonly reported adverse events (AEs). Some participants reported ophthalmic complaints, but a causal relationship with 3BNC117 was not established. No SAEs or grade 3/4 AEs deemed related to 3BNC117 occurred. A safety data summary is included in the Investigator's Brochure (IB).

Preliminary PK data show that 3BNC117's half-life is 17.6 days in HIV-uninfected and 9.6 days in viremic HIV-infected individuals. 3BNC117 decay rates following first and second infusions appear to be similar.

When administered at 30 mg/kg, 3BNC117 induced rapid decreases in plasma HIV-1 RNA levels that varied between individuals from 0.8 to 2.5 log₁₀ copies/ml. The median time to reach the nadir in viremia was 7 days, and the mean drop in VL was 1.48 log₁₀ copies/ml at nadir. Emergence of resistant viral strains was variable, with some individuals remaining sensitive to 3BNC117 for a period of 28 days after infusion (Caskey, Klein et al. 2015).

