7.1 Regimen

3BNC117 and 10-1074 will be administered intravenously at 3 or 10 mg/kg.

- Group 1: one infusion of 3BNC117 and 10-1074 at day 0, each dosed at 10 mg/kg.
- Group 2: three infusions of 3BNC117 and 10-1074, each dosed at 3 mg/kg, at day 0, weeks 8 and 16.
- Group 3: three infusions of 3BNC117 and 10-1074, each dosed at 10 mg/kg, at day 0, weeks 8 and 16.

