8.1 Analysis of Safety, PK and Antiretroviral effects

Primary Outcomes

- Safety: The safety population will include all participants who receive placebo or 3BNC117 and 10-1074 infusions. A baseline measurement and at least one laboratory, vital sign, or other safety-related measurement obtained after placebo or 3BNC117 and 10-1074 infusions may be required for inclusion in the analysis of a specific safety parameter.

The number and percentage of participants experiencing one or more AEs will be summarized by study group, relationship to study drug, and severity. AEs will be summarized by the number and percentage of participants who experienced the event, according to system organ class (SOC) and preferred term. AEs will also be summarized by severity grade and by relationship to study drug according to the Toxicity Grading Scale for Healthy Adult and Adolescent Volunteers Enrolled in Preventive Vaccine Clinical Trials. The CTCAE v4.03 grading scale will be used for reporting and grading adverse events related to infusion reactions and cytokine release syndromes in all groups (**Appendix B**). Changes in hematology, chemistry, and other laboratory values will be summarized descriptively. Changes will be calculated relative to the values collected at baseline.

- Pharmacokinetic parameters will be calculated using standard non-compartmental analysis methods. Descriptive results will be presented for the pharmacokinetic parameters by the 3 study groups. Pharmacokinetic parameters, including AUC, Cmax, $t_{1/2}$, Tmax and others will be summarized using descriptive statistics. ANOVA model will be used to compare group differences for AUC and Cmax. Regression analyses will be performed with AUC and Cmax as dependent variables and dose group as an independent variable. Population intrinsic factors, such as weight and gender, will be included in the regression models to assess whether these factors modify the relationship between dose and pharmacokinetic parameters.

Secondary outcomes

- Anti-10-1074 antibodies: The frequency of induced anti-3BNC117 and anti-10-1074 antibodies at 8 weeks following each infusion will be reported for all 3 groups and the proportion will be compared using Fisher's Exact test. The levels of the anti-antibodies will be compared using ANOVA or Kruskal-Wallis test.

Exploratory measurements

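### Anti-drug antibodies are analysed only 8 weeks after each infusion, when drug that could mask them may still circulate; a reading at the final visit would guard against this at little cost

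*Protocol*

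**What the plan says.** The secondary objective in Protocol section 3.5 carries no time limit: "To assess the frequency and magnitude of induced anti-3BNC117 and anti-10-1074 antibodies". Section 3.6 turns it into an outcome with a fixed time: "Frequency and levels of induced anti-3BNC117 and anti-10-1074 antibodies at 8 weeks after each infusion in all study groups". Section 8.1 repeats that time: "The frequency of induced anti-3BNC117 and anti-10-1074 antibodies at 8 weeks following each infusion will be reported for all 3 groups". It compares the proportions with Fisher's exact test and adds, for magnitude, "The levels of the anti-antibodies will be compared using ANOVA or Kruskal-Wallis test". Neither section names another reading.

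The groups differ in dose and number of infusions (section 7.1). Group 1 receives "one infusion of 3BNC117 and 10-1074 at day 0, each dosed at 10 mg/kg". Groups 2 and 3 receive three infusions of each antibody, at weeks 0, 8 and 16, at 3 and 10 mg/kg respectively.

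Two passages give the persistence of drug in HIV-uninfected people, both marked preliminary. For 3BNC117 the "half-life is 17.6 days in HIV-uninfected and 9.6 days in viremic HIV-infected individuals" (section 3.3.4). For 10-1074 the "half-life in HIV-uninfected individuals is approximately 15.5 days" (section 3.4.4).

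On follow-up, section 4 says: "Study participants will be followed for a total of 24 weeks following the final antibody infusion". Section 6.2.5 has blood drawn at every visit. Section 6.2.11.4 names the laboratory for the anti-drug antibody assay but gives no format, sensitivity or drug tolerance. The visit schedule in Appendix A is not among the pages at hand.

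**The concern.** Drug in the sample can bind anti-drug antibody and keep an assay from detecting it. Week 8 is only 3.2 half-lives (56/17.6) after an infusion of 3BNC117 and 3.6 half-lives (56/15.5) after one of 10-1074, so a measurable amount of each should remain. A negative result at that time could mean either no response or a masked one.

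Any masking would also be uneven. At the same infusion number, the 10 mg/kg groups carry more residual drug than the 3 mg/kg group, and these are the groups that section 8.1 compares. A lower frequency at 10 mg/kg could then reflect the assay rather than the dose.

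Immunogenicity is the only secondary objective, and the protocol already brings every participant back at a time when almost no drug should be left.

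**Working it through.** The protocol states no figure for residual drug or for expected anti-drug antibody frequency, so there is no stated number to reproduce.

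**Inputs from the protocol.** Half-lives of 17.6 days (section 3.3.4) and 15.5 days (section 3.4.4); infusions 56 days apart and doses of 3 and 10 mg/kg (section 7.1); last contact at 168 days after the last infusion (section 4); six active participants per group (section 4).

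**Residual fraction.** Assuming single-exponential decay from the peak, the fraction left after t days is 2^(−t/half-life). Write r for its value at 56 days.

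- 3BNC117: r = 2^(−56/17.6) = 0.110, or 11.0%.
- 10-1074: r = 2^(−56/15.5) = 0.082, or 8.2%.

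Eight weeks after the third infusion, all three doses contribute r + r² + r³ of a single-dose peak:

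- 3BNC117: 12.4%.
- 10-1074: 8.9%.

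At 168 days the fraction is r³ after one infusion and r³ + r⁴ + r⁵ after three:

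- 3BNC117: 0.13% and 0.15%.
- 10-1074: 0.055% and 0.06%.

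The drop from week 8 to week 24 is 1/r², about 80-fold for 3BNC117 and 150-fold for 10-1074.

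**Difference between doses.** The fraction is the same at both doses, but the amount differs by 10/3 = 3.3. In time, that equals half-life × log2(10/3): 17.6 × 1.737 = 30.6 days for 3BNC117 and 15.5 × 1.737 = 26.9 days for 10-1074.

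**Concentration (illustration only).** The protocol gives no volume of distribution. With an assumed initial volume of 40 to 80 ml/kg, 8 weeks after an infusion leaves about 3 to 9 µg/ml at 3 mg/kg and 10 to 31 µg/ml at 10 mg/kg. At 24 weeks after the third infusion it is below 0.4 µg/ml at either dose.

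**Effect on frequency (illustration only).** Take an assumed true rate of 30% at both doses and assumed assay sensitivities at 3 and 10 mg/kg. The reading is 0.30 × sensitivity, and the expected count is six times that.

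| Sensitivity, 3 vs 10 mg/kg | Frequency read | Expected positives of 6 |
|---|---|---|
| 95% vs 90% | 28.5% vs 27% | 1.71 vs 1.62 |
| 90% vs 60% | 27% vs 18% | 1.62 vs 1.08 |
| 80% vs 40% | 24% vs 12% | 1.44 vs 0.72 |

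Even in the last row, the spurious difference is under one participant in six.

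**Power of the planned comparison.** Between two groups of six, Fisher's test gives p = 0.061 for 0/6 vs 4/6 and p = 0.015 for 0/6 vs 5/6.

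**Which readings could be improved.** In Groups 2 and 3, week 8 after infusions 1 and 2 is the day of the next infusion. No sample between those infusions has less drug. Only the reading after the last infusion (the only one in Group 1) can be supplemented by a later one.

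**The case against.** The strongest objection is that the harm rests on a property the protocol does not give. Residual drug matters only if the assay fails at those concentrations. If it tolerates roughly 10 to 30 µg/ml (on the assumed volume), the effect disappears. This stands: a reader might infer that frequency is understated and the dose comparison biased, but the document supports only that both may happen.

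Second, a reader might infer that no later sample is taken. Sampling is set in Appendix A, which is not shown and may schedule later anti-drug antibody samples. What is established is narrower: the defined outcome and its analysis use only the 8-week reading, so later samples would fall outside both.

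Third, week 8 is already the lowest-drug time after infusions 1 and 2 in Groups 2 and 3. This stands, and limits the point to the period after the last infusion.

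Fourth, the consequences are modest. Section 8.1 treats inference as exploratory, six active participants per group make the comparison weak whatever the assay does, and neither the gate between groups in section 4 nor the review triggers in section 13.1 uses anti-drug antibodies. This stands, and it lowers the importance of the point.

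Fifth, it is tempting to conclude that the group comparison should move to the final visit. The document does not support that. Responses may wane over 24 weeks, so a late reading alone could also understate frequency.

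Finally, the half-lives are preliminary, and decay from the peak ignores any distribution phase. The 8 to 12% is therefore towards the upper end as a share of peak. The 3.3-fold dose ratio does not depend on the half-life, provided kinetics are the same at both doses.

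**Conclusion.** The point holds in a limited form. Sections 3.6 and 8.1 tie the only secondary objective to one time after each infusion. On the protocol's own half-lives, about 8 to 12% of a single-dose peak may remain then, with 3.3 times as much at 10 as at 3 mg/kg. A negative result after the last or only infusion therefore cannot be read cleanly unless the assay's drug tolerance is known, and any masking would be greater at 10 mg/kg.

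This assumes single-exponential decay, the preliminary half-lives, equal kinetics at both doses and an assay that residual drug can affect. The last is unknown, so actual bias is not shown. The main exposure is the descriptive frequency rather than a test result, and importance is low to moderate. The change is worth making because it is cheap and uses a visit that already exists.

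**What to change.** In sections 3.6 and 8.1:

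- Keep the 8-week readings.
- Add a reading of anti-3BNC117 and anti-10-1074 antibodies at the final visit, 24 weeks after the last infusion.
- Count a participant as positive if positive at any post-baseline reading.
- Show the three-group comparison at the final visit beside the 8-week comparison, not in place of it.
- Report the serum drug level at each reading next to the result, and state the assay's drug tolerance if it is known.

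Cost: one more run per antibody per participant. That is 24 × 2 = 48 runs, or 26 × 2 = 52 with the over-enrolment of two allowed in section 10, on blood drawn at an existing visit. If Appendix A already schedules this sample, only the outcome and analysis text needs to change.

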5.1 Inclusion Criteria

- 1. Males and females, age 18 to 65.
- 2. Amenable to HIV risk reduction counseling and agrees to maintain behavior consistent with low risk of HIV exposure.
- 3. If sexually active male or female, and participating in sexual activity that could lead to pregnancy, agrees to use two effective methods of contraception (i.e. condom with spermicide, diaphragm with spermicide, hormone-eluting IUD, hormone-based contraceptive with condom) for the duration of the study.

5.2 Exclusion Criteria

- 1. Confirmed HIV-1 or HIV-2 infection.
- 2. History of immunodeficiency or autoimmune disease; use of systemic corticosteroids, immunosuppressive anti-cancer, or other medications considered significant by the trial physician within the last 6 months.
- 3. Any clinically significant acute or chronic medical condition (such as autoimmune diseases) that in the opinion of the investigator would preclude participation.

- 4. Within the 12 months prior to enrollment, the participant has a history of sexually transmitted infection.
- 5. Chronic Hepatitis B or Hepatitis C infection.
- 6. Laboratory abnormalities in the parameters listed:
 - a. Absolute neutrophil count $\leq 2,000$;
 - b. Hemoglobin ≤ 12 gm/dL if female; ≤ 13.5 gm/dL if male;
 - c. Platelet count $\leq 125,000$;
 - d. ALT \geq 1.25 x ULN; AST \geq 1.25 x ULN;
 - e. Alkaline phosphatase $\geq 1.5 \times ULN$
 - f. Total bilirubin > 1.0 x ULN;
 - g. Creatinine $\geq 1.1 \text{ x ULN}$;
- 7. Pregnancy or lactation.
- 8. Any vaccination within 14 days prior to infusion
- 9. Receipt of any experimental HIV vaccine in the past.
- 10. History of severe reaction to a vaccine or drug infusion or history of severe allergic reactions.
- 11. Participation in another clinical study of an investigational product currently or within past 12 weeks, or expected participation during this study.

6 Methods and Procedures

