6.2.11.5 Pharmacokinetic evaluations

3BNC117 and 10-1074 serum levels will be measured by validated sandwich ELISA methods performed at Celldex Therapeutics. Serum samples will be collected before and at the end of each 3BNC117 and of each 10-1074 infusion, at 2 days and 1, 2, 3 and 4 weeks after respective infusions, and at later time points as outlined in **Appendix A**.

Briefly, serum samples, positive and negative controls, and multiple dilutions of a 3BNC117 or 10-1074 reference standard will be incubated in plates coated with a murine anti-idiotype antibody to 3BNC117 or a murine anti-idiotypic antibody to 10-1074 for the respective assays. Immobilized 3BNC117 will be detected with a murine anti-human IgG kappa chain mAb-HRP conjugate, and immobilized 10-1074 will be detected with an affinity-purified $F(ab')_2$ fragment goat polyclonal anti-human IgG Fc gamma chain specific-HRP conjugate. Colorimetric detection will be afforded with HRP substrate, tetra-methylbenzidine.

The concentration of 3BNC117 or 10-1074 in the samples will be interpolated from a standard curve of 3BNC117 or 10-1074, using a logistic curve-fitting algorithm. The reference standard and positive controls will be created from the drug product lot of 3BNC117 or 10-1074.

Pharmacokinetic parameters, including AUC, Cmax, $T_{1/2}$, Tmax and others will be estimated by performing a non-compartmental analysis (NCA) using WinNonlin 6.3. ANOVA model will be used to compare cohort differences for AUC and Cmax. The dose proportionality for the 2 parameters (AUC and Cmax) will be examined by regression analysis. Exposure parameters will be compared between single-and multiple-dose regimens to evaluate the extent of drug accumulation and the impact on clearance. Pharmacokinetic parameters will be examined to correlate exposure with safety and pharmacodynamic parameters (decline in plasma HIV-1 RNA), and variance, based on population intrinsic factors such as weight and gender, will be explored. In addition, we will compare pharmacokinetic parameters when 3BNC117 and 10-1074 are given in combination to historical monotherapy data with either antibody.

7 Investigational Products

Investigational Drug Name:	3BNC117
Manufacturer name of drug:	Celldex Therapeutics, Inc.
IND Number:	118,225
IND Sponsor:	[name]
Investigational Drug Name:	10-1074
Manufacturer name of drug:	Celldex Therapeutics, Inc.
IND Number:	123,713
IND Sponsor:	[name]

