The PI and sponsor (Rockefeller University) are the owners of the data. The PI will take primary responsibility for the data. Data will first be collected on paper charts and then transferred into a secure online database managed by the Emmes Corporation. Access to the Emmes website is granted only after an authorized individual (e.g., PI, Study Coordinator or supervising monitor at Rockefeller University) grants permission and a staff member completes a roster form stating his or her study role/responsibilities and contact information. Access to the data system requires a different username and password from the Emmes website, and access can be tailored based on the user's role/ responsibilities in the study. The only protected health information entered into the Emmes database is participants' DOB. This is done in order to confirm that a participant meets age-eligibility criteria. DOB is then converted to age and does not appear on any data summaries sent from Emmes. All Emmes websites use SSL for secure transport. The clinical study team will have access to the Emmes database, however, only a single study team member will input data into the database. Changes to the database are tracked by user and time of entry. Password-protected data summaries that contain no protected health information are released to the PI from Emmes through ELF and will be secured on the PI's encrypted password protected computer. Study team members may also store these data summaries on their own encrypted password-protected computers.

De-identified blood samples will be sent to a collaborator at Beth Israel Deaconess and the resulting data will be returned by email to the PI. The Exchange email system will be used by our collaborator to report the result of the assay. These reports contain no protected health information.

10 Recruitment and Advertising

Both men and women ages 18 through 65 will be recruited for the study from the community at large and will be referred by physicians in the community. We will make every effort to recruit minorities and women.

We project screening 72 participants in order to achieve at least 24 evaluable participants. In case of drop-outs an over-enrollment of 10% (2 participants) will be allowed.

Advertisements – The RUH Clinical Research Support Office (CRSO) will utilize the Volunteer Repository. Advertisements will also be placed: online (e.g. Craiglist, Centerwatch, etc), in newspapers (Metro, AMNY) and on campus.

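### Exclusion 9 bars past experimental HIV vaccines, but nothing bars past 3BNC117 or 10-1074 after 12 weeks, so a previously dosed volunteer can enter a trial of induced anti-drug antibodies

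*Protocol*

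**What the plan says.** Protocol 5.2, item 9, excludes "Receipt of any experimental HIV vaccine in the past"; the synopsis repeats it. Item 11 excludes "Participation in another clinical study of an investigational product currently or within past 12 weeks, or expected participation during this study". Item 10 excludes "History of severe reaction to a vaccine or drug infusion or history of severe allergic reactions". No item in 5.1, 5.2 or the synopsis names earlier receipt of 3BNC117, 10-1074 or another anti-HIV antibody. Section 6.2.4 specifies vaccination reactions and contraceptive practice as history to be taken, and does not mention earlier antibody receipt.

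The protocol shows that such people exist. Section 3.3.4 gives 22 HIV-uninfected participants in the 3BNC117 phase 1 study and adds: "Five HIV-uninfected individuals received two infusions of 3BNC117 at 30 mg/kg, 12 weeks apart." Section 3.4.4 says of the 10-1074 study that "23 participants (12 HIV-uninfected, 8 viremic HIV-infected and 3 ART-treated HIV-infected individuals) have enrolled in the study". Section 10 states: "The RUH Clinical Research Support Office (CRSO) will utilize the Volunteer Repository."

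The affected outcomes are in 3.5, 3.6 and 6.2.11.5. The secondary outcome is "Frequency and levels of induced anti-3BNC117 and anti-10-1074 antibodies at 8 weeks after each infusion in all study groups". The primary safety objectives concern a single infusion of the combination and three infusions of it. PK parameters are to be compared when the two antibodies are "given in combination to historical monotherapy data with either antibody".

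**The concern.** The criteria shut out permanently anyone exposed to a different class of product, yet admit someone exposed to the very antibodies being tested once 12 weeks have passed. A time window clears drug from the blood. It cannot be assumed to clear an immune response to the drug.

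Three things are at stake:

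- **Anti-drug antibodies.** In a previously dosed participant, a positive result 8 weeks after an infusion cannot be attributed cleanly to this trial's infusions.
- **Safety by number of infusions.** Such a person in Group 1 is not a single-exposure participant. Someone who had two 3BNC117 infusions earlier and then completes Group 2 or 3 has had 2 + 3 = 5, not three.
- **Historical PK comparison.** The same person could stand on both sides of it.

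Eligibility is fixed in the protocol. Once one of six active places has been used, no analysis can turn that participant into a first-exposure one.

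**Working it through.** **Inputs.** Each group has 8 participants, 6 active and 2 placebo (4 and 6.2.2), so 18 are active in all. Half-lives in HIV-uninfected people are 17.6 days for 3BNC117 (3.3.4) and about 15.5 days for 10-1074 (3.4.4). Follow-up in both earlier studies is 24 weeks after the last or only infusion (same sections). Item 11 gives 12 weeks = 84 days.

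**The protocol's own precision figures.** Table 1 in 8.2 is the exact two-sided 95% upper limit with no events, 1 − 0.025^(1/n):

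- n = 6: 1 − 0.025^(1/6) = 0.459, printed as 0.46
- n = 18: 1 − 0.025^(1/18) = 0.185, printed as 0.19

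All 15 entries reproduce.

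**Weight of one person.** A previously dosed entrant has a 6/8 = 75% chance of active product. If that person's anti-drug antibody result is positive because of the earlier exposure:

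| Denominator | Without | With | Shift |
|---|---|---|---|
| One group, n = 6 | 0/6, upper limit 46% | 1/6, upper limit 64% | 16.7 points |
| Pooled active, n = 18 | 0/18, upper limit 19% | 1/18, upper limit 27% | 5.6 points |

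**Residual drug**, assuming simple exponential decay, fraction left = 2^(−days/half-life):

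- 84 days: 3BNC117 2^(−84/17.6) = 3.7%; 10-1074 2^(−84/15.5) = 2.3%
- 24 weeks of follow-up plus 12 weeks = 252 days: 3BNC117 2^(−252/17.6) = 0.005%; 10-1074 2^(−252/15.5) = 0.001%

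**Chance that it happens.** The documents give no share of past recipients among entrants. If the share were f, the chance of at least one among n active participants would be 1 − (1 − f)^n:

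| Assumed f | n = 6 | n = 18 |
|---|---|---|
| 0% | 0% | 0% |
| 2% | 11% | 30% |
| 5% | 26% | 60% |
| 10% | 47% | 85% |

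These shares are illustrative only.

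**Candidates lost by the fix.** 22 + 12 = 34 HIV-uninfected participants, if nobody was in both studies. Section 10 projects 72 screenings.

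**The case against.** Much can be said against a strong version of this point, and most of it stands.

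- **Residual drug.** A reader might infer serious carry-over: an earlier 30 mg/kg dose followed by 3 mg/kg here gives 3.7% × 30/3 = 37% of the new starting level for 3BNC117, and 2.3% × 10 = 23% for 10-1074. That requires someone who left the earlier study almost at once after dosing and entered Group 2 exactly 12 weeks later. After completed follow-up the residue is negligible, and the PK sample taken before the first infusion (section 4) would show any that remained.
- **Altered clearance.** A reader might infer faster clearance on re-exposure. Section 3.3.4 reports that 3BNC117 decay looked similar after first and second infusions. That evidence is preliminary and covers 3BNC117 only, but nothing in the protocol points the other way.
- **Re-exposure hazard.** Section 3.1.2 mentions severe hypersensitivity after re-exposure, but for palivizumab, at under 1 per 100,000 recipients and also after first doses. Item 10 removes past severe reactors. The documents do not support a claim of material added risk.
- **Re-entry from Group 1.** Item 11 speaks of another study, so a literal reader might see a route from Group 1 into a later group. With 24 participants, eight per group, and participants blinded until the end, the protocol does not contemplate one person filling two places.
- **Baseline antibody sample.** Appendix A is not shown and may schedule one. It would identify entrants who already have anti-drug antibodies. It would not keep them out, need not detect immune memory without circulating antibody, and would not restore first-exposure safety data.
- **Item 2** lets the trial physician exclude for other significant medication within 6 months. It is discretionary and time-limited, so it does not close the gap.
- **Stakes.** Section 8.1 calls the analysis mainly descriptive and hypothesis-generating, and repeat dosing is planned in two of the three groups.

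What survives is the gap in eligibility and its effect on the anti-drug antibody proportions and on the count of exposures.

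**Conclusion.** The point holds as a cheap improvement. As written, the criteria admit a past recipient of 3BNC117 or 10-1074 after 12 weeks, provided the person had no severe reaction and meets the other criteria. One such participant on active product weighs 17 percentage points in a group's anti-drug antibody frequency or 5.6 points pooled, blurs the single-infusion and three-infusion safety descriptions, and may also belong to the PK comparator.

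The size rests on two assumptions: that at least one past recipient applies, and that earlier dosing left an immune response. The documents establish neither. The number of applicants may be zero, no anti-drug antibody finding is reported for earlier recipients of either product, and section 10 does not say that the repository lists past antibody recipients. A reader should not infer that the PK results would be distorted by leftover drug or changed clearance, or that participants face a demonstrated extra hazard.

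**What to change.** In exclusion 9, in both 5.2 and the synopsis, insert after the word *vaccine*: *, or of 3BNC117, 10-1074 or another anti-HIV-1 monoclonal antibody,*. Add one question on earlier receipt of such antibodies to the telephone pre-screen (6.1.1).

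The cost is one phrase in two places and one question. About 34 known HIV-uninfected past recipients of the two products are lost as candidates, plus any recipients of other anti-HIV-1 monoclonal antibodies. That is a small loss when 72 people are to be screened from the community at large. Sample size, regimen and analyses are unchanged.
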